5.3.3.2. Infusion-Related Reactions of Grade 3 (severe) or Higher

For IRR adverse events (other than laryngeal edema or bronchospasm) that are Grade 3, the daratumumab administration must be stopped and the subject must be observed carefully until resolution of the adverse event or until the intensity of the event decreases to Grade 1, at which point the daratumumab administration may be restarted at the investigator's discretion. If the intensity of the adverse event returns to Grade 3 after restart of the daratumumab administration, then the subject must be withdrawn from daratumumab treatment.

For IRR adverse events that are Grade 4, the daratumumab administration must be stopped and the subject withdrawn from daratumumab treatment.

5.3.3.3. Recurrent Infusion-Related Reactions

If a Grade 3 IRR (or Grade 2 or higher event of laryngeal edema, or a Grade 2 or higher event of bronchospasm) recurs during or within 24 hours after a subsequent daratumumab administration, the daratumumab treatment must be discontinued.

6. TREATMENT COMPLIANCE

6.1. Dose Delays and Dose Modification

Dose modification of daratumumab is not permitted, but dose delay is the primary method for managing daratumumab-related toxicities.

6.1.1. Daratumumab-Related Toxicity Management

Refer to Section 5.3 for details on management of IRRs. The study treatment must be held if any of the following criteria below are met, to allow for recovery from toxicity, regardless of relationship to daratumumab. The criteria for a dose delay are:

1. Grade 4 hematologic toxicity, except for grade 4 lymphopenia
2. Grade 3 thrombocytopenia with bleeding
3. Febrile neutropenia
4. Neutropenia with infection, of any grade
5. Grade 3 or higher non-hematologic toxicities with the following exceptions:
 - a. Grade 3 nausea that responds to antiemetic treatment within 7 days
 - b. Grade 3 vomiting that responds to antiemetic treatment within 7 days
 - c. Grade 3 diarrhea that responds to antidiarrheal treatment within 7 days
 - d. Grade 3 fatigue that was present at baseline or that lasts for <7 days after the last administration of daratumumab
 - e. Grade 3 asthenia that was present at baseline or that lasts for <7 days after the last administration of daratumumab.

Administration of daratumumab may be restarted upon recovery from toxicity to Grade 2 or better or baseline, with the exception that Grade 2 laryngeal edema or Grade 2 bronchospasm must be fully recovered.

If a daratumumab administration does not commence within the prespecified window (Table 3) of the scheduled administration date, then the dose will be considered a missed dose. Administration may resume at the next planned dosing date. A missed dose will not be made up.

Table 3: Daratumumab-Related Toxicity Management

Cycles	Frequency	Dose Held	Dosing Restart*
1 and 2	Weekly (Q1W)	>3 days	next planned weekly dosing date
3 to 6	Biweekly (Q2W)	>7 days	next planned biweekly dosing date
7+	Every 4 weeks (Q4W)	>14 days	next planned every 4 weeks dosing date

*Dosing on Day 1 of a cycle must not be skipped.

Cycles may be delayed up to 4 weeks (Cycle 1 to Cycle 6) or up to 6 weeks (Cycle 7 and beyond). If a dose is delayed on Day 1 of a cycle, then the dates of all the subsequent doses should be adjusted accordingly to maintain the 28-day cycle duration. However, if a within-cycle dose is delayed, then the dates of the subsequent doses should **not** be adjusted.

Any AE deemed to be related to daratumumab that requires a dose hold of more than 4 weeks (Cycle 1 to Cycle 6) or more than 6 weeks (Cycle 7 and beyond) will result in permanent discontinuation of daratumumab. If a dose delay occurs, then PK and pharmacodynamic assessments should be performed on the actual administration day of daratumumab, not on the original scheduled administration day.

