4.4. Extent of Exposure

Extent of exposure to study treatment will be summarized and presented based on all treated population.

The number and percentage of subjects treated within each cycle will be summarized. The maximum number of treatment cycles received for each subject will be summarized by frequency and descriptive statistics.

Duration of study treatment, defined as the number of days from the date of the first administration of study treatment to the date of the last administration of study treatment, will be summarized. The number of daratumumab infusions will be summarized for all treated subjects.

Daratumumab dose intensity, which is defined as the sum of total dose administered (mg/kg) in all cycles divided by the number of treatment cycles, will be summarized. Additionally, the daratumumab dose intensity will be summarized for cycles with high-intensity (Cycles 1-2) or low-intensity (Cycles 3-6 and Cycles 7+).

The relative dose intensity (%) defined as the ratio of total actually received dose and total planned dose will be calculated and summarized using descriptive statistics.

The number of subjects with cycle delays or dose modifications (dose delays or dose skipping) including reasons (AE or other) for cycle delays or dose modifications, will be reported.

A listing of subjects with daratumumab infusions will be provided.

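### From Cycle 7 every dose is a Day 1 dose, so for holds of 15 to 42 days the missed-dose rule in Protocol 6.1.1 contradicts the Table 3 footnote and the delay text

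*Protocol*

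**What the plan says.** All the conflicting text is in Protocol 6.1.1 (Daratumumab-Related Toxicity Management).

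- **Missed-dose sentence.** If an infusion does not start within its Table 3 window, "then the dose will be considered a missed dose"; treatment may pick up again on the following scheduled date, and the lost infusion is not replaced.
- **Table 3.** A dose is missed when held more than 3 days (Cycles 1 and 2), more than 7 days (Cycles 3 to 6) or more than 14 days (Cycle 7 onward). Dosing then restarts on the "next planned weekly dosing date", the "next planned biweekly dosing date" or the "next planned every 4 weeks dosing date" respectively.
- **Footnote.** An asterisk on the restart column leads to: "Dosing on Day 1 of a cycle must not be skipped".
- **Text below the table.** It reads "Cycles may be delayed up to 4 weeks (Cycle 1 to Cycle 6) or up to 6 weeks (Cycle 7 and beyond". A late Day 1 dose moves every later dose; a late within-cycle dose moves none.

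Protocol 6.1.2, on holds not suspected to be drug-related, treats the Table 3 window as the time allowed, then applies the same 4-week and 6-week limits before discontinuation. No section says which rule prevails for a Day 1 dose.

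SAP 4.4 (Extent of Exposure) will report "The number of subjects with cycle delays or dose modifications (dose delays or dose skipping", with reasons, and relative dose intensity as total received dose over total planned dose.

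**The concern.** From Cycle 7 the Time and Events Schedule has one infusion per cycle, on Day 1. The Cycle 7+ row of Table 3 can therefore apply only to doses that the footnote says may not be skipped. If the row is followed, the footnote is breached. If the footnote is treated as an exception, the row governs no dose at all.

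A site managing a hold of, say, three weeks in Cycle 9 has two incompatible instructions: drop the dose and wait for the next 4-weekly date, or give it on recovery and re-date what follows. The patient's next infusion date depends on the choice. So does whether SAP 4.4 counts the event as a skip or a delay.

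**Working it through.** The plan states no figure to reproduce. The check counts which doses each Table 3 row can govern, then compares the two rules hold by hold.

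**Inputs.** 28-day cycles (Protocol 5). Infusion days 1, 8, 15 and 22 in Cycles 1 and 2, days 1 and 15 in Cycles 3 to 6, and Day 1 only from Cycle 7 (Time and Events Schedule). Missed-dose thresholds and delay limits are from Protocol 6.1.1.

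**Step 1: doses under each row, and Day 1 holds covered by both rules**

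| Cycles | Doses | Day 1 | Within-cycle | Missed if held | Delay allowed to | Overlap for Day 1 |
|---|---|---|---|---|---|---|
| 1–2 | 2 × 4 = 8 | 2 | 6 | > 3 days | 28 days | 4–28 days |
| 3–6 | 4 × 2 = 8 | 4 | 4 | > 7 days | 28 days | 8–28 days |
| 7+ | 1 per cycle | 1 | 0 | > 14 days | 42 days | 15–42 days |

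If the footnote exempts Day 1, the first two rows still govern 6 and 4 within-cycle doses. The third governs none.

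**Step 2: next dosing date in Cycle 8 or later.** Let the previous dose be day 0, the planned dose day 28, and the hold *h* days. The ±3-day scheduling window is ignored.

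- *Delay rule:* dose on day 28 + *h*.
- *Missed-dose rule, h = 15 to 27:* the dose is dropped and the next planned date is 28 + 28 = day 56. The delay rule gives 28 + 15 = 43 to 28 + 27 = 55. The gap is 56 − 43 = 13 days down to 56 − 55 = 1 day.
- *h = 28:* both rules give day 56.
- *Missed-dose rule, h = 29 to 42:* the subject is still on hold on day 56, so that next dose is itself late by *h* − 28 = 1 to 14 days. This is within its own window, so it is given on day 56 + (*h* − 28) = 28 + *h*, that is day 57 to 70. The delay rule gives the same days.

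For Cycle 7 Day 1 the previous infusion is Cycle 6 Day 15, 14 days earlier. The figures for holds of 15 to 27 days become 14 + 28 = 42 days if skipped and 14 + 15 = 29 to 14 + 27 = 41 days if delayed. The gap is again 13 down to 1 day.

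**Step 3: effect on relative dose intensity for one such hold**

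- Cycles 1 to 12, skipped dose counted as planned: 8 + 8 + 6 = 22 planned, so 21/22 = 95.5% if skipped and 22/22 = 100% if delayed.
- Cycles 7 to 12 only, same convention: 5/6 = 83% against 6/6 = 100%.
- Planned dose counted only over treated cycles (SAP 2.5 requires a non-zero dose): 21/21 = 100% if skipped, the same as if delayed.

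SAP 4.4 does not define total planned dose, so the documents do not settle which result applies.

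**The case against.** The strongest reply is that the section can be read coherently. The asterisk is on the restart column, so the footnote qualifies every row, and the next paragraph distinguishes Day 1 delays from within-cycle delays. The footnote is mandatory, while the restart sentence is permissive. On this reading Day 1 doses are always delayed and Table 3 governs only within-cycle doses. That stands for Cycles 1 to 6, where the only gap is that precedence is not stated. It does not rescue Cycle 7 onward, because the row would then have nothing to govern.

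A reader might infer that patients get different dosing across the whole range of 15 to 42 days. Step 2 shows otherwise: dates differ only for 15 to 27 days, by 1 to 13 days.

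A reader might also infer that results stop being comparable between sites. SAP 2.2 pools all centres and no between-site comparison is planned. What remains is that the pooled counts of skips and delays could mix two conventions.

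Protocol 6.1.2 offers a partial safeguard, since over-long holds must be raised with the sponsor promptly. It excludes holds for toxicity suspected to be drug-related, which are the main subject of 6.1.1.

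**Conclusion.** For Cycle 7 onward, the dosing instruction for holds of 15 to 42 days contradicts itself and cannot be obeyed as written. The practical difference is limited. For holds of 15 to 27 days the next infusion moves by 1 to 13 days. For 28 to 42 days the date can coincide, and only the missed or delayed label and the cycle numbering change. These figures assume an otherwise on-schedule subject who is dosed as soon as the hold ends under the delay rule, and on the next planned date, or on recovery if later, under the missed-dose rule.

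The SAP 4.4 counts of delays and skips depend on which rule was followed. Whether relative dose intensity does too depends on how planned dose is counted, so no single percentage can be attached to the defect.

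It might be inferred that the primary result is at risk. The documents do not support that: the sample size of 32 and the response thresholds (at most 1 of 15 at stage 1, at least 8 of 32 at the end) do not depend on this rule, and the exposure summaries are descriptive outputs of a single-arm study.

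**What to change.** The sponsor should reconcile five pieces of text so that each length of hold of a Day 1 dose has one stated consequence: the missed-dose sentence, the Cycle 7+ row of Table 3, its footnote, the 4-week and 6-week delay text, and the reference in Protocol 6.1.2 to Table 3 as the allowed time. For Cycles 1 to 6, a statement of which rule takes precedence on Day 1 is enough. Which clinical rule applies is the sponsor's decision.

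SAP 4.4 should then define a delayed dose and a skipped dose in the same terms, and say whether total planned dose includes a skipped cycle.

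The cost is a wording change in the next protocol amendment and matching definitions in the SAP. No change to the sample size or the planned efficacy analyses is needed.

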6.1.2. Daratumumab Interruption or Missed Doses

A daratumumab dose that is held for more than the permitted time (Table 3) from the per-protocol administration date for any reason other than toxicities suspected to be related to daratumumab should be brought to the attention of the sponsor at the earliest possible time. Subjects whose dose was delayed for more than 4 weeks (Cycle 1 to Cycle 6) or 6 weeks (Cycle 7 and beyond) should have study treatment discontinued, unless, upon consultation with the sponsor and the review of safety and efficacy, continuation is agreed upon.

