9.2. Discontinuation of Study Treatment/Withdrawal From the Study

Discontinuation of Study Treatment

If a subject's study treatment must be discontinued, it will not result in automatic withdrawal of the subject from the study. The EoT Visits and Follow-up visit assessments should continue as specified in the [T&E Schedule](#).

A subject's study treatment (daratumumab) should be discontinued if:

- The investigator believes that for safety reasons or tolerability reasons (eg, AE) it is in the best interest of the subject to discontinue study treatment
- The subject becomes pregnant
- The subject withdraws consent for administration of study drug
- The subject initiates treatment with a prohibited medication
- The subject received concurrent (non-protocol) treatment for NKTCL
- The subject experiences unacceptable toxicity, including IRRs described in [Section 5.3](#)

- The subject's dose of daratumumab is held for more than 4 weeks in Cycles 1-6 or for more than 6 weeks in Cycle 7 and beyond (unless sponsor approves continuation)
- The subject experiences PD (see below and [Attachment 6](#)). Relapse from CR is not considered as disease progression.
- Daratumumab becomes commercially available (or when daratumumab can be accessed from another source) for this disease. At this time, the subject will be transitioned from study drug to commercial product and will be withdrawn from the study. In these circumstances, the sponsor and investigator will support transition of the subject to ensure that treatment continues and remains uninterrupted.
- A subject who experiences a second primary malignancy that cannot be treated by surgery or radiotherapy alone must be withdrawn from the study. However, a subject who develops a malignancy that can be cured surgically or with definitive radiotherapy may continue to receive the assigned study treatment and should continue to be followed for subsequent progression of NKTCL.

Subjects should be discontinued from study treatment if they have objective radiological PD based on real time BICR according to LUGANO Classification. Following centrally confirmed radiological PD subjects will be discontinued from study treatment and enter the Follow-up phase.

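### The hold-length bullet in Section 9.2 lets the sponsor approve continuation whatever the cause, while Section 6.1.1 requires permanent discontinuation when the cause is a daratumumab-related AE

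*Protocol*

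**What the plan says.** Protocol Section 6.1.1 covers toxicity management. Its rule on long holds begins "Any AE deemed to be related to daratumumab that requires a dose hold of more than 4 weeks", sets the limit at 6 weeks from Cycle 7 onwards, and says that such an event "will result in permanent discontinuation of daratumumab". It provides for no sponsor approval or other exception.

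Protocol Section 9.2 lists the circumstances in which daratumumab should be stopped. One bullet covers a dose held beyond 4 weeks in Cycles 1-6 or "for more than 6 weeks in Cycle 7 and beyond (unless sponsor approves continuation"). The bullet does not mention why the dose was held.

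Protocol Section 6.1.2 covers interruptions and missed doses. Its first sentence concerns a dose "held for more than the permitted time (Table 3) from the per-protocol administration date" and says that such a hold "for any reason other than toxicities suspected to be related to daratumumab should be brought to the attention of the sponsor". Its second sentence applies to "Subjects whose dose was delayed for more than 4 weeks (Cycle 1 to Cycle 6) or 6 weeks (Cycle 7 and beyond") and calls for discontinuation "unless, upon consultation with the sponsor and the review of safety and efficacy, continuation is agreed upon".

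**The concern.** Sections 6.1.1 and 9.2 set the same limits on a hold but differ on what may follow. Section 6.1.1 makes stopping automatic for related AEs. Section 9.2 makes stopping the default and allows the sponsor to override it, without excluding related AEs.

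This is a safety stopping rule, and 9.2 is where a reader looks for the reasons to discontinue. Site staff or a sponsor physician working from 9.2 alone would find a route to re-expose a subject after prolonged drug-related toxicity, although 6.1.1 closes that route. If continuation were approved on that basis, it would also be unclear whether to record a protocol deviation.

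**Working it through.** There is no calculation to reproduce; the check is a comparison of text. The limits are 4 weeks = 28 days in Cycles 1-6 and 6 weeks = 42 days from Cycle 7.

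| Protocol text | Limit on the hold | Cause covered | Consequence | Exception |
|---|---|---|---|---|
| 6.1.1 | >28 / >42 days | AE deemed related to daratumumab | Permanent discontinuation | None |
| 9.2, hold-length bullet | >28 / >42 days | None named, none excluded | Treatment should stop | Sponsor approval |
| 6.1.2, second sentence | >28 / >42 days | None named in that sentence | Treatment should stop | Agreed continuation after sponsor consultation |

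**Step 1: test case.** A subject is held for 5 weeks (35 days) in Cycle 3 for an AE deemed related. Since 35 > 28, both 6.1.1 and the 9.2 bullet are triggered. Under 6.1.1 the subject stops permanently. Under 9.2 the subject may continue if the sponsor approves. The permission in 9.2 is one that 6.1.1 withholds.

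**Step 2: does another 9.2 bullet close the gap?** Two other bullets have no sponsor exception. One begins "The investigator believes that for safety reasons or tolerability reasons" and depends on the investigator's judgement. The other covers unacceptable toxicity and points to Section 5.3 for infusion reactions. Neither states a hold length, so neither reproduces the automatic stop. Section 6.1.1 also allows a restart once toxicity has recovered to Grade 2 or better or to baseline. For an AE that recovers late, the hold-length rule may be the only remaining bar.

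**Step 3: does 9.2 lead the reader to 6.1.1?** Section 9.2 refers to the Time and Events Schedule, Section 5.3, Attachment 6, Section 8.1.4 and Section 15.2.3. It does not refer to 6.1.1 or 6.1.2, and no order of precedence is stated.

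**Step 4: does the SAP settle it?** No. SAP Section 4.4 reports cycle delays and dose modifications with their reasons, but sets no rule on continuation.

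**Step 5: is 6.1.2 a second conflict?** Its first sentence excludes suspected related toxicity. That sentence has its own trigger (the Table 3 windows of >3, >7 or >14 days) and its own duty (informing the sponsor). The second sentence does not repeat the exclusion. However, it follows directly and deals with longer delays, which fits an escalation from notifying to stopping. The section also comes straight after the one on related toxicity. The natural reading is that both sentences concern non-related holds.

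**The case against.** The strongest reply is that the two sections can be followed together. Section 9.2 says treatment should stop and only leaves room for sponsor approval; it entitles nobody to continue. A site and sponsor that obey 6.1.1 also comply with 9.2, and a specific mandatory rule ordinarily prevails over a general list. The sponsor wrote 6.1.1 and would have to approve continuation against its own rule. Section 16.1 separately requires sponsor contact before a non-emergency departure from the protocol. The most serious infusion reactions have their own mandatory stopping rules in Section 5.3.3, with no sponsor exception.

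Much of this stands, and it keeps the point small. It does not remove the point. The specific-over-general reading is plausible but is nowhere stated. Sponsor involvement is not an independent safeguard here, because sponsor approval is exactly the exception that 6.1.1 does not grant. The infusion-reaction rules do not cover other related AEs.

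A reader might go further and infer that 6.1.2 also contradicts 6.1.1, because the sponsor exception in its second sentence names no cause. The documents do not support counting this as a second contradiction: the opening of 6.1.2 and its place after 6.1.1 point to non-related holds. The 9.2 bullet has no such lead-in, so the point rests on 9.2 alone.

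**Conclusion.** The point holds for the hold-length bullet in Section 9.2, which is wrong as written: its sponsor exception reaches related-AE holds for which 6.1.1 requires permanent discontinuation.

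It is minor. Only subjects with a related AE and a hold beyond 28 or 42 days are affected, and only if the sponsor agrees to continue. The documents give no expected number of such subjects, so none is estimated here. Sample size, error rates and the ORR analysis do not depend on the bullet.

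The conclusion assumes that 6.1.1 is meant as it reads, with no exception for related AEs. Nothing in the protocol or SAP suggests otherwise.

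**What to change.** In the 9.2 bullet, replace the parenthesis with wording such as: *(the sponsor may agree to continuation under Section 6.1.2, but not where the hold is for a daratumumab-related AE; see Section 6.1.1)*.

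Optionally, state in the second sentence of 6.1.2 that it concerns holds for reasons other than daratumumab-related toxicity. This would only make the existing reading explicit.

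If the sponsor does want discretion over related AEs, the exception belongs in 6.1.1, with its conditions. Tightening 9.2 is the more protective choice and matches 6.1.1 as it stands.

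The cost is one clause and a cross-reference at the next amendment, with no new procedure, data or analysis.

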6.1.2. Daratumumab Interruption or Missed Doses

A daratumumab dose that is held for more than the permitted time (Table 3) from the per-protocol administration date for any reason other than toxicities suspected to be related to daratumumab should be brought to the attention of the sponsor at the earliest possible time. Subjects whose dose was delayed for more than 4 weeks (Cycle 1 to Cycle 6) or 6 weeks (Cycle 7 and beyond) should have study treatment discontinued, unless, upon consultation with the sponsor and the review of safety and efficacy, continuation is agreed upon.

7. CONCOMITANT THERAPY

All prior oncologic therapies, including those since diagnosis, must be recorded at screening. Throughout the study, investigators may prescribe any concomitant medications or treatments deemed necessary to provide adequate supportive care except for those listed in Section 7.3. The sponsor must be notified in advance (or as soon as possible thereafter) of any instances in which prohibited therapies are administered.

Routine systemic use of concomitant medications will be collected in the electronic case report form (eCRF) and recorded in the source documents beginning with signing of the ICF to 30 days after the last dose of the last study treatment or until the start of subsequent anticancer treatment, if earlier. Concomitant medications to manage AEs and SAEs will be recorded as per Section 7.1.

Modification of an effective preexisting therapy should not be made for the explicit purpose of entering a subject into the study.

